Aim 2a: To assess the fidelity of the PIVOT with MI intervention. We will videotape a proportion of provider visits with VHPs at intervention practices to observe adherence to the intervention. We hypothesize that intervention providers will use PIVOT with MI techniques in >80% of encounters.

Aim 3: To evaluate the impact of the PIVOT with MI intervention on parent and provider experience.

experience. We will use a cross-sectional survey design to assess visit experience of VHPs at intervention and control practices. We will conduct pre-, interim - and post-intervention surveys of intervention and control providers to assess time spent and self-efficacy in discussing vaccines with VHPs. We hypothesize that VHPs at intervention visits will have a higher-rated experience than VHPs at control practices and intervention providers will spend less time and have improved self-efficacy in vaccine discussions with VHPs compared to control providers. Additionally, due to implications of COVID-19 on research and health care delivery, a new survey will better help the study team understand the extent of the impact of COVID-19 on the delivery of health supervision visits at our pediatric clinics, specifically on infant vaccine delivery and uptake.

The proposed study uses a rigorous design to test an innovative, evidence-based provider communication strategy to address a critical public health problem. We plan to use our results to inform future dissemination and implementation work conducted within the American Academy of Pediatrics' Pediatric Research in Office Settings network and the American Academy of Family Physicians' National Research Network.

RESEARCH STRATEGY

A. SIGNIFICANCE

The reduction of vaccine-preventable diseases (VPDs) is a top public health priority in the US today.¹⁹ Parental refusal or delay of childhood vaccines is a key contributor to the persistence of outbreaks of VPD²⁰ and is associated with higher inpatient admission and ED utilization rates,²¹ increased morbidity,²²⁻²⁴ and death.²⁵ There is therefore renewed emphasis on sustaining and improving childhood vaccine coverage.^{11,26} [ENREF 25](#)

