C.6.e. Covariate-constrained Randomization: Practices will be the unit of randomization. A key issue in cluster-randomized trials is the possibility of covariate imbalance in practices assigned to different treatment arms.¹⁰⁴⁻¹⁰⁸ Thus, practices will be randomly assigned to assure balanced comparison groups using optimized probability sampling to the intervention or control arm in the following manner. From the pool of practices that agree to participate in the study, pre-study information will be collected on several characteristics that may influence study outcomes: percent of VHPs, percent of Vaccines-for-Children [VFC]-eligible patients, number of pediatric providers, and practice immunization rates of children 19-35 months old. These pre-study variables will then be used to develop and evaluate a balance criterion, defined as the sum of the squared differences between standardized practice means on these variables.¹⁰⁵ All possible combinations of eligible practices in 2 arms (intervention and control) will be generated using a SAS macro program.¹⁰⁷ The distribution of the balance criterion for the 2 study arms will be used to define an acceptable set of study arms that are reasonably balanced in terms of the selected variables (minimum 10% of balance criterion).¹⁰⁵ From this set, one set will be chosen at random and used to randomly assign each practice to intervention or control arms. This process will be undertaken in both Colorado and Washington as separate randomization procedures. We have successfully used covariate-constrained randomization in C.1.d. and other studies.^{109,110}

We will perform the following procedures to obtain pre-study information on these covariates:

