age for 6 vaccines combined (Hepatitis B, DTaP, Hib, IPV, MMR, and Varicella).¹⁸ This corresponds to an average of 37 days late per vaccine dose. To be able to detect with adequate power ($\geq 90\%$) a decrease in under-immunization of 10 days—a decrease that has the potential to be clinically meaningful since 27 days would not be considered late for most vaccines because of the 30 day window in which most vaccine doses are recommended¹²¹—we need to enroll 600 VHP/newborn pairs total, with 300 per arm and 25 at each of the 24 study practices (assuming an α of 0.05, a SD of 20, and an intraclass correlation coefficient for within-clinic correlation of 0.02²⁸). Assuming a 10% prevalence of VHPs (see C.1.b),²⁸ we will need to approach 6,000 parents to reach our sample size goal. This is feasible to achieve in our designated 18 month recruitment period given our design to integrate PACV-SF screening of parents of newborns into standard practice workflow and our estimate (determined by spot chart reviews at PSPRN and COCONet practices) that there are ≥ 10 newborns per clinic per week in PSPRN and COCONet practices. If we vary our assumptions regarding VHP prevalence (7.5%) or SD (25), we would need to approach 8,000 and 12,000 parents, respectively, for adequate ($\geq 90\%$) power to detect the same effect size, both of which remain feasible within the 18 month enrollment period assuming ≥ 10 newborns per clinic per week. If we have unbalanced enrollment across study arms (i.e. not 1:1 enrollment in intervention and control arms), we will continue enrollment beyond 600 VHP/newborn pairs total in order to reach at least 300 VHP/newborn pairs per arm given the impact of an imbalance on our power.

For our fidelity outcome (Aim 2a), power can be considered in terms of the number of videotaped interactions needed to develop this coding scheme. Based on our prior studies (see C.1.c.), 3 videotaped visits per provider should be adequate to achieve sufficient behavioral variation across providers. We will therefore videotape up to 360 encounters (up to 180 in each state), which averages to 3 videotaped encounters per practice provider.

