C.7.d. Analysis: Since there is no optimal method for summarizing parent experience, we will use 2 dichotomization methods: the top-box method,¹²⁵⁻¹²⁸ consistent with Consumer Assessment of Healthcare Providers and Systems survey scoring,¹²⁹ and an alternative method^{123,130,131} in which an average score of ≥ 6 (out of 7) on each of the 15 items is indicative of a highly rated visit experience.¹⁶ We will also summarize parent experience as a continuous variable. We will use Pearson's χ^2 test to compare parent (binary) ratings of visit experience between control and intervention arms. We will apply mixed effects logistic regression model to account for within-clinic correlation and any unbalanced confounding factors. When summarizing parent experience as a continuous variable, we will apply Box-Cox transformation if it is highly skewed and linear mixed effect models similar to Equation (1) to examine differences between control and intervention arms.

For the provider outcomes, we will compare the pre- and post-intervention proportions of control and intervention providers who (1) spent <10 minutes vs. 10+ minutes discussing vaccines at a typical visit and during visits with parents who had vaccine concerns; (2) used the presumptive and/or MI techniques in vaccine discussions with families (always, frequently, sometimes, never); and (3) perceived they were able to influence parents' vaccine decisions (Appendix 3). We will use Pearson's χ^2 test for an unadjusted analysis of the pre-post differences between control and intervention arms and multivariable logistic regression for adjusted analyses that control for potential confounding variables such as provider demographic and practice characteristics. Planned subgroup analyses include examining outcomes by practice type (public/private), %VHPs in the practice, and number of practice providers. Models will account for clustering of outcomes by practices where needed.

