C.7.e. Power calculation: For the parent visit experience outcome, we will have 80% power to detect a 13 percentage point difference in the proportion of parents who rate their visit experience highly between control and PIVOT with MI practices if we enroll 312 VHPs (156 per arm) assuming a baseline proportion of 72% of parents who rate their visit experience highly [ENREF 17¹⁶](#) and equal distribution of participants in control and PIVOT with MI practices. For each of the provider outcomes, we will have 80% power to detect a 12 percentage point pre-post difference between control (1 percentage point pre-post difference) and intervention providers (13 percentage point pre-post difference), assuming 60 providers in each arm. Overall, this number of providers per arm for these provider outcomes seems feasible since we anticipate the proposed study will involve >120 total providers (5-7 providers per practice).

C.7.f. Strengths and Limitations: We are only including VHPs who give us permission to contact them. There may be differential participation rates among VHPs in the control and intervention arms, resulting in unequal distribution and bias. Though we will account for this in our analysis, our results may nonetheless not be generalizable to parents and children with less access to health care and to parents less likely to participate.

C.8. Future Directions

We have designed the proposed study with dissemination in mind. Study materials will be developed so that they may be easily adapted to other settings, with particular focus on having the online video module available for use by others immediately (see *C.5.e.*). In addition, should this intervention prove effective, we intend to collaborate with 2 national PBRNs—the AAP PROS Network and the AAFP NRN—to test the intervention on a broader scale (*see letters of support from the directors of PROS and NRN*).

C.9. Study Timeline

Project Task	Year 1				Year 2				Year 3				Year 4				Year 5			
	1	2	3	4	1	2	3	4	1	2	3	4	1	2	3	4	1	2	3	4
Quarters																				
1) Obtain all needed Institutional Review Board approvals	1	2	3	4																
2) Recruit PSPRN and COCONet practices	1	2	3	4																
3) Develop PIVOT with MI provider training program	1	2	3	4																
4) Obtain MOC-4 approval for PIVOT with MI program	1	2	3	4																
5) Data collection for covariates in balanced randomization																				

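### The 80% power for parent visit experience (C.7.e) makes no allowance for clustering by practice; it is about 71% if the ICC is 0.02

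*Combined protocol and SAP*

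**What the plan says.** - **Power (C.7.e).** The plan claims "80% power to detect a 13 percentage point difference in the proportion of parents who rate their visit experience highly", "if we enroll 312 VHPs (156 per arm) assuming a baseline proportion of 72% of parents who rate their visit experience highly", and "equal distribution of participants in control and PIVOT with MI practices". It gives no ICC, design effect or number of practices for this outcome, and it does not state alpha or the direction of the difference.
- **Hypothesis (Aim 3).** The expected direction is an increase: "VHPs at intervention visits will have a higher-rated experience than VHPs at control practices".
- **Design (C.6.e).** "Practices will be the unit of randomization".
- **Analysis (C.7.d).** A Pearson chi-square compares the binary ratings between arms. Then: "We will apply mixed effects logistic regression model to account for within-clinic correlation and any unbalanced confounding factors". The section does not say which of the two carries the inference.
- **Primary outcome (C.6.k).** Here the plan does allow for clustering, with a within-clinic ICC of 0.02. It plans "300 per arm and 25 at each of the 24 study practices".

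**The concern.** The plan recognizes clustering in the randomization, in the primary power calculation and in the analysis model for visit experience. The power statement for visit experience is the one place where it is missing. Parents at the same practice share providers and, in the intervention arm, the same training. Any positive within-practice correlation therefore leaves 156 parents with less information than 156 independent ones.

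C.7.a explains why this outcome is measured: in preliminary work the presumptive format was associated with lower odds of a highly rated visit. A null result could be read as reassurance that visit experience is preserved. Overstated power makes that reading look safer than it is.

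**Working it through.** **Inputs**

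- Proportions: 72% (C.7.e) and 72% + 13 points = 85%, an increase as Aim 3 hypothesizes.
- Parents: 156 per arm, 1:1 (C.7.e).
- Alpha: 0.05, from C.6.k ("assuming an α of 0.05, a SD of 20"), since C.7.e states none. Two-sided is assumed.
- Practices: 24 (C.6.k), so 12 per arm and 156/12 = 13 VHPs per practice, assumed equal.
- ICC: none is given for visit experience. The 0.02 in C.6.k is borrowed, and 0.005 to 0.05 is an assumed range.

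**Step 1: reproduce the plan's figure without clustering**

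Use the two-proportion formula with pooled variance under the null and no continuity correction. The mean proportion is 0.785.

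n = [1.96·√(2·0.785·0.215) + 0.8416·√(0.72·0.28 + 0.85·0.15)]² / 0.13² = 155.6, so 156 per arm.

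Power(n) = Φ{[0.13·√n − 1.96·√(2·0.785·0.215)] / √(0.72·0.28 + 0.85·0.15)} = Φ{[0.13·√n − 1.139] / 0.574}.

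- n = 156: 80.1%
- n = 155: 79.9%

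The plan's number is matched exactly and leaves no room for a design effect. A decrease of 13 points (72% to 59%) would need 209 per arm, so 156 fits only the increase.

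**Step 2: add clustering**

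Design effect = 1 + (13 − 1)·ICC, and effective n = 156 / design effect. Effective n goes into the power formula of Step 1. The last column is the number per arm that restores 80% power for 72% versus 85% with the practices fixed at 12 per arm. It solves n / [1 + (n/12 − 1)·ICC] = 155.6, which gives n = 155.6·(1 − ICC) / (1 − 155.6·ICC/12).

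| ICC | Design effect | Effective n per arm | Power, 72% vs 85% | Increase detectable at 80% power | VHPs per arm for 80% power |
|---|---|---|---|---|---|
| 0.005 | 1.06 | 147.2 | 77.8% | 13.3 points | 166 |
| 0.01 | 1.12 | 139.3 | 75.5% | 13.7 points | 177 |
| 0.02 | 1.24 | 125.8 | 71.1% | 14.3 points | 206 |
| 0.05 | 1.60 | 97.5 | 60.0% | 16.0 points | 420 |

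**Step 3: related checks**

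- The first three targets fit within the 300 VHPs per arm of C.6.k (206/300 = 69%). The last does not: 300 per arm at ICC 0.05 (25 per practice, design effect 1 + 24·0.05 = 2.2) gives about 75%.
- For a 13-point decrease (72% to 59%), 156 per arm gives 68% power without clustering and 58% at ICC 0.02.
- A t reference with 22 degrees of freedom (24 practices less 2) and unpooled variance gives about 68% at ICC 0.02, against 77% by the same method without clustering. Unequal numbers per practice would lower power further.

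**The case against.** The best case for leaving C.7.e alone has four parts.

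- **The ICC is borrowed.** C.6.k cites its 0.02 to the earlier clinic-randomized trial described in C.1.b, which studied parental hesitancy rather than visit experience. At ICC 0.005 the loss is only about 2 points, and balanced randomization and covariate adjustment may reduce between-practice variance. This stands as a caution against treating 71% as the answer. It does not rescue the 80%, which needs an ICC of essentially zero.
- **The analysis is sound.** The mixed model accounts for clustering, so only the advertised power is wrong. This is correct, and it limits the severity.
- **312 is a condition, not a cap.** C.7.e says what power follows if that many enroll, and more parents could be surveyed. True, but the power attached to that number is still overstated.
- **A larger target may be hard to reach.** Parents must permit contact and then agree to the survey. The only interest figure in the documents is for videotaping, above 70% (C.6.g). If 70% applied to the survey, 206/0.70 = 294 of 300 VHPs per arm (98%) would have to permit contact, against 156/0.70 = 223 (74%) for the present target. This stands, and it favors restating the power over raising the target.

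**Conclusion.** The concern holds. The 156 per arm in C.7.e is an individually randomized sample size presented as 80% power in a trial that randomizes practices. That conclusion does not depend on any particular ICC.

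The size of the shortfall does. It is about 9 points of power at ICC 0.02 (71% instead of 80%), and power ranges from 78% to 60% over ICC 0.005 to 0.05. These figures assume a two-sided alpha of 0.05, 12 practices per arm, equal yield of 13 VHPs per practice, an increase from 72% to 85%, and a normal approximation.

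The effect is confined to an Aim 3 secondary outcome. The plan should be corrected, but the main result of the trial is not at risk.

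**What to change.** Restate the power in C.7.e, for example:

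> With 156 VHPs per arm in 12 practices per arm (about 13 per practice), two-sided alpha 0.05, and an assumed ICC of 0.02 (the value used in C.6.k, since none is available for visit experience), power to detect an increase from 72% to 85% is about 71% (78% at ICC 0.005, 60% at ICC 0.05). The increase detectable with 80% power is about 14.3 points. For a 13-point decrease, power is about 58%.

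This changes wording only, at the price of a less favorable stated power. The sentence on a decrease is optional, but useful given the concern about lower ratings in C.7.a.

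In C.7.d, add a clarification:

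> Between-arm inference for the binary ratings rests on the mixed effects logistic model; the Pearson chi-square is descriptive.

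The alternative is to keep 80% and raise the target to about 206 per arm (17 to 18 per practice) at the same assumed ICC. That is 412 surveys instead of 312: 100 more, or 100 × $20 = $2,000 in the gift cards of C.7.c, plus staff time for calls. It works only if enough VHPs permit contact and respond, so restating the power is the safer choice.

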C.6. Aim 2: To evaluate the impact of the PIVOT with MI intervention on child immunization status at 19 months of age.

C.6.a. Overview and Design: We propose to conduct a cluster RCT (Figure 3). We will randomize PSPRN and COCONet practices (N=24) to control and intervention arms using a covariate-constrained randomization approach. All parents of newborn infants receiving health supervision at a study practice will be screened for vaccine hesitancy at their child's initial visit using the PACV-SF (see C.1.a.) in order to identify VHPs, the primary study population. Providers at intervention practices will receive the proposed 5-component PIVOT with MI provider training program (see C.5.b.). Providers at control clinics will give usual care. A subset of VHPs at intervention clinics who give us permission to contact them will have their child's health supervision visit videotaped to assess intervention fidelity. Our main outcome will be child immunization status at 19 months expressed as the mean percentage of days under-immunized from birth to 19 months.

[figure not shown]
C.6.b. Setting and Population: Two regional PBRNs (PSPRN and COCONet) from 2 states (Washington and Colorado) will serve as the study setting (see C.2.). Both Washington and Colorado are ideal settings to conduct a study of an intervention designed to improve immunization rates among VHPs because both have a high prevalence of VHPs, with each ranking in the highest quintile among US states with respect to the proportion of parents claiming non-medical exemptions for their child from required school-entry vaccines.²

C.6.c. Eligibility: Providers will be eligible if they belong to PSPRN or COCONet. All English- and Spanish-speaking parents with a newborn infant <1 month old receiving health supervision at a participating practice during the intervention period will be eligible. VHPs, defined as those who have a positive PACV-SF (see C.1.a.), will constitute our primary study population because we are most interested in changing their vaccination behavior.^{10,27} VHPs at intervention practices who indicate on the PACV-SF that study staff can contact them about participation in additional study activities will be eligible for the fidelity study (Aim 2a).

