At the conclusion of the video module window, providers will be asked to attend a 90 minute interactive in-person training session led by study staff. Attendance will be required for MOC Part 4 credit. This baseline training session will involve a baseline assessment of provider skills with the communication techniques introduced in the module and teaching and reinforcement of the PIVOT with MI strategy using modeling, role-playing and coaching by the study team. Providers will also receive instructions on how to use the reference sheets developed in Aim 1. Each intervention practice will have its own in-person training session. For PSPRN practices, sessions will be led by [name], [name], [name], and [name]. For COCONet practices, sessions will be led by [name], [name], and [name]. Based on our previous work, provider participation rate in this baseline training is expected to be $\geq 70\%$ (see *C.1.b.* and *C.1.d.*). The intervention period will commence at the conclusion of this baseline training and last 36 months (constituting the 18 month parent recruitment period [see *C.6.k.*] and the 18 months after this period to allow for the last enrolled newborn to reach 19 months old).

Six months into the intervention period, providers will receive a 60 minute in-person refresher training led by the same study team members. This will take a similar format to the initial training but will start with providers sharing their experiences with the PIVOT with MI intervention over the prior 6 months, with demonstrations from each provider of a difficult vaccine conversation with feedback from the MI trainer. At 12 months into the intervention period, we will have a second 90 minute in-person refresher training that will also include viewing 3-5 selected videotaped encounters of 2, 4 and/or 6 month health supervision visits involving intervention providers (with their permission) from the preceding 12 months (see *C.6.g.*) to illustrate “dos and don’ts” of the PIVOT with MI strategy. We will ask providers at the refresher training what they thought went well and what could be improved after watching each videotape. Study champions (1 per practice) will support the PIVOT with MI strategy throughout the remainder of the intervention period by soliciting periodic feedback from providers on use of the intervention and addressing implementation issues with the study team.

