visit if the parent gave their contact information on the PACV survey and agreed to be contacted to potentially participate in future research. A RA will call and contact the parent to gauge interest in the survey and if so, will proceed with administering the survey either via an emailed link or over the phone, while the RA will enter their answers in real time in REDCap. Once the survey is completed, the parent will receive a \$20 gift card as a thank you.

To assess provider time, communication approach, and self-efficacy in discussing vaccines with parents, we will administer surveys to all study providers at baseline, after the completion of the trainings in the intervention practices and at study completion. Baseline surveys will also include items querying provider demographic and practice characteristics. The survey instrument will be modified from a survey used in the PCOM project (see *C.1.d.*) and pilot tested (Appendix 3). The interim and post study surveys will have the same questions for both intervention and control providers, with a few additional questions evaluating the PIVOT with MI trainings and experiences among intervention providers only. Administration will be by paper or electronically, depending on practice preference. Participants will receive a \$25 gift card for participation. In previous studies with similar methods, we've achieved 87-95% provider response rates.

An additional survey taken by each of our pediatric clinics will better help us understand the impact of COVID-19 on health supervision visits and vaccine delivery and uptake. This survey will be administered in the summer months of 2020.

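### C.7.e takes its 60 providers per arm from a headcount of just over 120, with no allowance for survey non-response, so at 120 providers the stated 80% power is not reached

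*Combined protocol and SAP*

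**What the plan says.** C.7.e (Power calculation) states that "we will have 80% power to detect a 12 percentage point pre-post difference between control (1 percentage point pre-post difference"), with the other arm described as "intervention providers (13 percentage point pre-post difference), assuming 60 providers in each arm". It supports that number by headcount alone: "this number of providers per arm for these provider outcomes seems feasible since we anticipate the proposed study will involve >120 total providers (5-7 providers" in each practice). C.6.a gives the number of practices: "We will randomize PSPRN and COCONet practices (N=24) to control and intervention arms".

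C.7.c (Data Collection and Implementation) surveys all study providers at three times: at baseline, once the trainings are finished, and at the end of the study. It then reports: "In previous studies with similar methods, we've achieved 87-95% provider response rates". C.7.d (Analysis) says "we will compare the pre- and post-intervention proportions of control and intervention providers", using a Pearson chi-square test on the pre-post differences between arms, followed by adjusted logistic models. On the interval between the surveys, C.6.f says: "The intervention period will commence at the conclusion of this baseline training and last 36 months".

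C.7.d does not say how to treat a provider with only one of the two surveys, a provider who leaves, or one who joins after baseline. The missing-data sentences in C.6.j stand in the analysis of parent data.

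**The concern.** Half of 120 is exactly 60. At that headcount the power statement holds only if every provider answers both the baseline and the completion survey. The plan's own response rates say this will not happen, and neither C.7.e nor C.7.d allows for it.

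Two things are at stake. The stated power is somewhat optimistic at the lower end of the expected headcount. Also, with no rule for who is analysed, the provider comparison can be run in more than one way once the data are in: on pairs only, or on everyone who answered before against everyone who answered after. In the second form leavers count only before and joiners only after, so the two groups being compared are partly different people. Providers who join an intervention practice after month 12 may have attended none of the in-person sessions, which C.6.f places at baseline, 6 and 12 months.

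**Working it through.** **Inputs.** Change of 1% (control) against 13% (intervention), 60 per arm, 80% power, and 5-7 providers per practice (C.7.e); 24 practices (C.6.a); response rate r = 0.87 to 0.95 (C.7.c); chi-square test (C.7.d). C.7.e gives no alpha. Two-sided 0.05 is assumed, the level that C.6.k gives for the primary outcome. No clustering allowance is applied.

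**Step 1: reproduce the plan's figure.** Treat each provider as carrying one pre-post score, with proportions 0.01 and 0.13. Sum the binomial probabilities of all pairs of counts for which the uncorrected Pearson chi-square rejects. At n = 60 per arm, power = 80.8%, which matches the stated 80%.

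This reading needs both surveys from each provider. Comparing unpaired cross-sections does not reproduce 80%. With the same baseline b in both arms, SE = sqrt[(2b(1-b) + (b+0.01)(1-b-0.01) + (b+0.13)(1-b-0.13))/60]. For b = 0.10 this is sqrt(0.455/60) = 0.0871, and 0.12/0.0871 - 1.96 = -0.58, so power is about 28%. For b = 0.50 it is about 15%. The baselines are assumed, as C.7.e gives none.

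**Step 2: headcount.** 24 x 5 = 120, 24 x 6 = 144 and 24 x 7 = 168 providers, or 60, 72 and 84 per arm.

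**Step 3: providers with both surveys.** If r applies at each survey:
- the same providers miss both: n = (per arm) x r;
- misses are independent: n = (per arm) x r², where 0.87² = 0.757 and 0.95² = 0.9025. Between 9.8% and 24.3% then lack at least one survey.

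| Providers per practice | Per arm | Same providers miss both | Independent misses |
|---|---|---|---|
| 5 | 60 | 52.2 to 57.0 | 45.4 to 54.2 |
| 6 | 72 | 62.6 to 68.4 | 54.5 to 65.0 |
| 7 | 84 | 73.1 to 79.8 | 63.6 to 75.8 |

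**Step 4: power by the method of Step 1.**
- Five per practice, same providers missing: 73.9% at 52, 78.4% at 57.
- Five per practice, independent: 71.4% at 45, 75.8% at 54.
- Six per practice, independent: 75.8% at 54, 84.4% at 65.
- Seven per practice, independent: 83.7% at 64, 90.3% at 76.

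Exact chi-square power does not rise smoothly with n (76.0% at 49, 71.9% at 50), so differences of a few points between neighbouring sample sizes should not be over-read.

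**Step 5: headcount that secures 60 scored per arm.** Under independence, 120/0.9025 = 133 and 120/0.757 = 159 providers (rounded up).

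**The case against.** The plan expects more than 120 providers and a range of five to seven per practice, and says only that 60 per arm seems feasible. At seven per practice the target is met. At six it is met if the same providers miss both surveys, and otherwise depends on the response rate. C.2.a adds some comfort for Washington: more than 100 pediatricians in 18 practices is above 5.5 per practice, before counting the nurse practitioners and physician assistants who are also eligible. All of this stands. It confines the certain shortfall to the floor of the range.

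C.7.c also does not say that its response rates are per survey. That reading is an assumption, and so is independence between surveys. At 120 providers, however, any response below 100% at each survey leaves fewer than 60 pairs per arm, so the conclusion there does not rest on independence.

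A reader might infer more than this: that turnover pushes power well below these figures, or that untrained joiners dilute the intervention effect so that a null provider result would reflect staff change. The documents do not support either as a finding. C.6.d mentions provider turnover as a possibility, but no section gives a rate for leavers or joiners, so any figure would be invented. Nor are later joiners shown to be unexposed. The intervention also includes an online module, reference sheets and a practice champion who continues after the last session, and C.6.f calls its own description preliminary. The supportable statement is that joiners may have missed the in-person trainings.

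Finally, C.7.d already plans adjusted models that account for practice clustering where needed, and the imputation sentence in C.6.j is not expressly limited to parents. Neither says which providers belong in the comparison.

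**Conclusion.** The point holds at the lower end of the planned headcount. C.7.e uses the expected number of providers as the analysed number. With 120 providers and 87-95% response at each survey, 60 scored per arm is missed whatever the overlap of non-response, and power is about 71-78% against the stated 80%. That is a loss of roughly 2 to 9 points from the 80.8% that the same calculation gives at 60 per arm. Near 144 providers the result depends on the response rate and its overlap; at 168 the target is met before turnover.

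This rests on the per-survey reading of the response rates, two-sided 0.05, one pre-post score per provider, and no clustering. It does not show that the provider outcomes are underpowered across the plan's whole range. The missing definition of the provider analysis set applies at any headcount. These are secondary outcomes, so the importance is minor to moderate.

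**What to change.** **C.7.e.** Restate the power for the number of providers expected to have both surveys, across five to seven per practice: about 45-57 per arm at five, 54-68 at six and 64-80 at seven, depending on overlap. Alternatively, state that about 133-159 enrolled providers are needed for 60 scored per arm under independence. Label the result as the power of the simple pre-post comparison. It is not the power of the mixed model below, which would need its own calculation. State the alpha.

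**C.7.d.** Define the main provider set as providers at the practice at baseline, whether or not they answered the baseline survey. Requiring a baseline answer would drop providers who missed only that survey. It could also introduce selection, because C.9 lists the baseline survey together with the training and after the covariate collection for randomization, so the survey may follow allocation. Analyse all available responses from this set in one repeated-measures logistic mixed model with an arm-by-time term and provider and practice effects. Report providers who joined later separately, since they may have missed the in-person trainings.

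**Cost.** Analysis wording, a less favourable stated power at the lower headcounts, and the loss of late joiners from the main comparison. No additional providers or surveys are required unless the sponsor chooses to secure 60 scored per arm.
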